#### **8.4.5     Pregnancy and Exposure During Breastfeeding**

Information in this section is not applicable since participants are infants.

#### **8.4.6     Disease-related Events and/or Disease-related Outcomes Not Qualifying as AEs or SAEs**

This is not applicable to this study.

#### **8.4.7     Events of Clinical Interest**

There are no events of clinical interest in this study.

## **8.5 Treatment of Overdose**

In this study, an overdose is the administration of more than 1 dose of any individual study vaccine in any 24-hour period.

No specific information is available on the treatment of overdose.

All reports of overdose must be reported by the investigator within 5 calendar days to the Sponsor either by electronic media or paper. Electronic reporting procedures can be found in the EDC data entry guidelines. Paper reporting procedures can be found in the Investigator Trial File Binder (or equivalent).

Decisions regarding dose interruptions or modifications will be made by the investigator in consultation with the Sponsor Clinical Director based on the clinical evaluation of the participant.

## **8.6 Pharmacokinetics**

Pharmacokinetics parameters will not be evaluated in this study.

## **8.7 Pharmacodynamics**

Pharmacodynamic parameters will not be evaluated in this study.

## **8.8 Biomarkers**

Biomarkers are not evaluated in this study.

### **8.8.1 Planned Genetic Analysis Sample Collection**

Planned genetic analysis samples will not be evaluated in this study.

### **8.9 Future Biomedical Research Sample Collection**

If the participant's parent or legally acceptable representative provides documented informed consent for future biomedical research, the following specimens will be obtained as part of future biomedical research:

- DNA for future research
- Leftover main study serum from immunogenicity assay stored for future research

## **8.10 Health Economics Medical Resource Utilization and Health Economics**

Medical resource utilization and health economics are not evaluated in this study.

## 8.11 Visit Requirements

Visit requirements are outlined in Section 1.3. Specific procedure-related details are provided in Section 8.

### 8.11.1 Screening

Screening procedures will be conducted at Visit 1 as outlined in Section 1.3. Potential participants will be evaluated to determine that they fulfill the entry requirements as set forth in Section 5. Screening procedures may be repeated after consultation with the Sponsor.

### 8.11.2 Treatment Period/Vaccination Visit

Requirements during the treatment period are outlined in Section 1.3.

### 8.11.3 Discontinued Participants Continuing to be Monitored in the Study

A participant may discontinue from study intervention (including receipt of V114), but continue to participate in protocol-specified, AE-monitoring activities as outlined in Section 1.3, as long as the participant's parent or legally acceptable representative does not withdraw consent. Blood draws for immunogenicity testing could occur if agreed to by the participant's parent or legally acceptable representative at the discretion of the investigator.

## 9 STATISTICAL ANALYSIS PLAN

This section outlines the statistical analysis strategy and procedures for the study. Changes to analyses made after the protocol has been finalized, but before final database lock, will be documented in an sSAP and referenced in the CSR for the study. Post hoc exploratory analyses will be clearly identified in the CSR.

### 9.1 Statistical Analysis Plan Summary

Key elements of the statistical analysis plan are summarized below; the comprehensive plan is provided in Sections 9.2 through 9.12.

Study Design Overview	A Phase 3, Single-Arm, Open-label Clinical Study to Evaluate the Safety and Immunogenicity of 4 doses of V114 Administered to Healthy Infants in South Korea
Treatment Assignment	Participants will be allocated to V114.
Analysis Populations	Immunogenicity: Per-Protocol Safety: All Participants as Treated

Primary Endpoint(s)	Immunogenicity: 
 
Anti-PnPs serotype-specific IgG response rates (proportion of participants with anti-PnPs serotype-specific IgG <math>\geq 0.35</math> <math>\mu</math>g/mL) at 30 days PD3
 
Anti-PnPs serotype-specific IgG GMCs at 30 days PD3
 
 Safety: 
 
Proportion of participants with solicited injection-site AEs (swelling, redness/erythema, tenderness/pain, and hard lump/induration) from Day 1 through Day 7 after vaccination with V114
 
Proportion of participants with solicited systemic AEs (irritability, drowsiness/somnolence, appetite lost/decreased appetite, and hives or welts/urticaria) from Day 1 through Day 7 after vaccination with V114
 
Proportion of participants with vaccine-related SAEs from Day 1 through completion of study participation
 

Key Secondary Endpoints	Anti-PnPs serotype-specific IgG GMCs at 30 days PD4
Statistical Methods for Key Immunogenicity Analyses	Immunogenicity analyses will be conducted for each of the 15 pneumococcal serotypes in V114 separately. To address the primary immunogenicity objectives, estimation of the IgG response rates and GMCs will include descriptive summaries and 95% CIs at 30 days PD3. A similar statistical approach will be used to evaluate the IgG GMCs at 30 days PD4.
Statistical Methods for Key Safety Analyses	The analysis strategy for safety parameters after each vaccination is described in Section 9.6.2. Safety parameters will be summarized via descriptive statistics. In addition, for select safety parameters, 95% CIs will be provided.
Interim Analyses	There are no planned interim analyses for this study.
Multiplicity	No multiplicity adjustment is planned.
Sample Size and Power	Immunogenicity: This study will allocate approximately 45 participants to V114. It is assumed that approximately 38 participants will be evaluable for immunogenicity analyses at 30 days PD3 (85% evaluability rate), and approximately 36 participants will be evaluable for immunogenicity analyses at 30 days PD4 (80% evaluability rate). There are no hypotheses to be evaluated, but Section 9.9.1 provides information about the expected variability of the IgG GMCs given the sample size.

## 9.2 Responsibility for Analyses/In-house Blinding

The statistical analysis of the data obtained from this study will be the responsibility of the Clinical Biostatistics department of the Sponsor.

This trial is being conducted as a nonrandomized, open-label study; ie, subjects, investigators, and Sponsor personnel will be aware of participant treatment assignments after each participant is enrolled and treatment is assigned.

The Clinical Biostatistics department will generate the treatment/randomization schedule(s) for study treatment assignment. Treatment/randomization will be implemented using an IRT system.

### **9.3 Hypotheses/Estimation**

Objectives of the study are stated in Section 3. This is an estimation study and no formal hypothesis testing will be performed.

### **9.4 Analysis Endpoints**

Immunogenicity and safety endpoints that will be summarized are listed below.

#### **9.4.1 Safety Endpoints**

Safety and tolerability will be assessed by clinical review of all relevant parameters including AEs and postvaccination temperature measurements after any vaccination with V114.

The safety endpoints include:

- Proportion of participants with solicited injection-site AEs (swelling, redness/erythema, tenderness/pain, and hard lump/induration) from Day 1 through Day 7 after any vaccination with V114
- Proportion of participants with solicited systemic AEs (irritability, drowsiness/somnolence, hives or welts/urticaria, and appetite loss/decreased appetite) from Day 1 through Day 7 after any vaccination with V114
- Proportions of participants with the broad AE categories consisting of any AE and a vaccine-related AE from Day 1 through Day 7 after any vaccination with V114
- Proportions of participants with an SAE, a vaccine-related SAE, and discontinuation due to an AE, and death from Day 1 through completion of study participation
- Participants body temperature measured from Day 1 through Day 7 after any vaccination with V114

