Nonstudy Pediatric Vaccines	(X)	(X)	(X)		(X)		Sponsor will not provide nonstudy pediatric vaccines, but they are permitted to be given during the study. If given at the same time, oral vaccines are recommended to be given before the study vaccine and other injectable vaccines. Other injectable vaccines are administered after the study vaccine and in a separate limb.  See Section 6.5 for details on concomitant vaccines.
Provide Paper VRC	X	X	X		X		A paper VRC will be provided to record AEs, body temperature, concomitant medications, and nonstudy vaccinations. Instructions for using the paper VRC will be reviewed with the participant's parent or legally acceptable representative.  See Section 8.1.9 and 8.3.3 for details regarding the completion of the paper VRC.
Collect Paper VRC and Review VRC data with Participant's Parent or Legally Acceptable Representative		X	X	X		X	See Section 8.1.9 for details.
Safety Procedures							
Complete Physical Examination	X						To be performed by the investigator or medically qualified designee before vaccine is administered (see Section 8.3.1).
Targeted Physical Examination		X	X		X		To be performed by the investigator or medically qualified designee before vaccine is administered (see Section 8.3.1).
Body Temperature Measurement	X	X	X		X		Each participant's body temperature must be taken before vaccination (see Section 8.3.2 for method). Participants who have febrile illness at or within 72 hours of vaccination must be rescheduled.

Study Period:	Intervention						Comments
Visit Number	1	2	3	4	5	6	
Scheduled Time:	Age: ~2 months (Dose 1)	Age: ~4 months (Dose 2)	Age: ~6 months (Dose 3)	~1 month after Dose 3	Age: ~12 to 15 months (Dose 4)	~1 month after Dose 4	Months of age is calculated according to the participant's birth date
Visit Window a	≥42 days of age to ≤90 days of age	4 months of age to 1 day before 5 months of age	6 months of age to 1 day before 7 months of age	Day 28 to Day 42 Postdose 3	12 months of age to 1 day before 16 months of age	Day 28 to Day 42 Postdose 4	
15-Minute Postvaccination Observation Period	X	X	X		X		The observation period can be extended if clinically indicated.
AE Monitoring	X	X	X	X	X	X	Nonserious AEs are to be reported from Days 1 through 14 after each vaccination. SAEs and deaths are to be reported throughout the duration of an individual's study participation.

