### 3 HYPOTHESES, OBJECTIVES, AND ENDPOINTS

The following objectives and endpoints will be evaluated in healthy infants enrolled at approximately 2 months of age (from 42 to 90 days [inclusive]) administered V114.

Objectives	Endpoints
Primary	

 
Objective 1: To evaluate the safety and tolerability of V114 with respect to the proportion of participants with adverse events (AEs).
 
	
 
Solicited injection-site AEs from Day 1 through Day 7 postvaccination.
 
Solicited systemic AEs from Day 1 through Day 7 postvaccination.
 
Vaccine-related serious adverse events (SAEs) through completion of study participation.
 

 
Objective: To evaluate the anti-pneumococcal polysaccharide (PnPs) serotype-specific Immunoglobulin G (IgG) response rates (proportion of participants meeting serotype-specific IgG threshold value of <math>\geq 0.35 \mu\text{g/mL}</math>) at 30 days after Dose 3.
 
Objective: To evaluate the anti-PnPs serotype-specific IgG Geometric Mean Concentrations (GMCs) at 30 days after Dose 3.
 
	
 
Anti-PnPs serotype-specific IgG responses for the 15 serotypes contained in V114 at 30 days Postdose 3 (PD3).
 

Secondary	

 
Objective: To evaluate the anti-PnPs serotype-specific IgG GMCs at 30 days after Dose 4.
 
	
 
Anti-PnP serotype-specific IgG responses for the 15 serotypes contained in V114 at 30 days Postdose 4 (PD4).
 

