### 8.3.3 Safety Assessment and Use of the Paper VRC

All participants will be observed for at least 15 minutes after each vaccination for any immediate reactions. The observation period can be extended if clinically indicated. If any immediate AEs are observed during this period, the time at which the event occurred within this timeframe, as well as the event itself, any concomitant medications that were administered, and resolution of the event, must be recorded on the appropriate eCRF.

The limb that was used for the administration of V114 will be recorded in the paper VRC (Note: the study will report injection-site AEs from V114 only, not from concomitant injectable vaccines; the location of V114 administration can be used by the participant's parent or legally acceptable representative to monitor the appropriate limb for injection-site AEs related to V114).

Participant's parent or legally acceptable representative will use the paper VRC (Section 8.1.9) to document the following information:

- Rectal/axial temperatures measured Day 1 (day of vaccination) through Day 7 after each vaccination
- Solicited injection-site AEs (swelling, redness, pain or tenderness, and hard lump) Day 1 through Day 7 postvaccination
- Solicited systemic AEs (irritability, drowsiness, appetite lost, and hives or welts) Day 1 through Day 7 postvaccination
- Any other unsolicited injection-site or systemic AEs Day 1 through Day 14 postvaccination
- Use of any analgesic or antipyretic on the day of vaccination
- Concomitant medications and nonstudy vaccinations Day 1 to Day 14 postvaccination

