### **8.4.1 Time Period and Frequency for Collecting AE, SAE, and Other Reportable Safety Event Information**

All AEs, SAEs, and other reportable safety events that occur after the participant provides documented informed consent but before treatment/randomization must be reported by the investigator if they cause the participant to be excluded from the study, or are the result of a protocol-specified intervention, including but not limited to washout or discontinuation of usual therapy, diet, placebo, or a procedure.

All AEs, SAEs, and other reportable safety events must be reported by the investigator from the day of allocation/randomization to the first vaccination and from the day of each vaccination through 14 days postvaccination. SAEs must also be reported throughout the duration of the individual's participation in the study, regardless of whether or not related to the Sponsor's product.

Additionally, any SAE brought to the attention of an investigator at any time outside of the time period specified in the previous paragraph also must be reported immediately to the Sponsor if the event is either:

- A death that occurs prior to the participant completing the study, but outside the time period specified in the previous paragraph.

OR

- An SAE that is considered by an investigator, who is a qualified physician, to be vaccine related.

Investigators are not obligated to actively seek AEs or SAEs or other reportable safety events in former study participants. However, if the investigator learns of any SAE, including a death, at any time after a participant has been discharged from the study, and he/she considers the event to be reasonably related to the study intervention or study participation, the investigator must promptly notify the Sponsor.

All initial and follow-up AEs, SAEs, and other reportable safety events will be recorded and reported to the Sponsor or designee within the time frames as indicated in [Table 2](#).

Table 2 Reporting Time Periods and Time Frames for Adverse Events and Other Reportable Safety Events

Type of Event	Reporting Time Period: Consent to Randomization/Allocation	Reporting Time Period: Randomization/Allocation through Protocol-specified Follow-up Period	Reporting Time Period: After the Protocol-specified Follow-up Period	Time Frame to Report Event and Follow-up Information to Sponsor:

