### 9.6.2 Statistical Methods for Safety Analyses

Safety and tolerability will be assessed by clinical review of all relevant parameters including AEs and postvaccination temperature measurements.

The analysis strategy of safety parameters is summarized in [Table 4](#). The proportion of participants with solicited injection-site AEs (swelling, redness/erythema, tenderness/pain, and hard lump/induration from Day 1 to Day 7 postvaccination) and solicited systemic AEs (irritability, drowsiness/somnolence, hives or welts/urticaria, and appetite loss/decreased appetite from Day 1 to Day 7 postvaccination) will be provided along with the corresponding CIs (based on the exact binomial method proposed by Clopper and Pearson [CLOPPER, C. J. and PEARSON, E. S. 1934]). In addition, the broad AE categories consisting of the proportion of participants with any AE, a vaccine-related AE, an SAE, a vaccine-related SAE, discontinuation due to an AE, and the proportion of participants who died will be summarized in the same manner. The proportion of participants with maximum temperature measurements meeting the Brighton Collaboration cut points (from Day 1 through Day 7) [Marcy, S. M., et al 2004] will also be provided along with the corresponding 95% CIs. Point estimates will be provided for all other safety parameters (specific AE terms and system organ class terms).

Medical device incidents due to syringe, if any, will be listed.

The safety parameters may be summarized separately as soon as complete data become available at 30 days after the third dose of V114 and 30 days after the fourth dose of V114.

Table 4 Analysis Strategy for Safety Parameters

Safety Endpoint	95% CI	Descriptive Statistics
Injection-site redness/erythema (Day 1 to Day 7) †	X	X
Injection-site swelling (Days 1 to 7) †	X	X
Injection-site tenderness/pain (Days 1 to 7) †	X	X
Injection-site hard lump/induration (Days 1 to 7) †	X	X
Irritability (Days 1 to 7) †	X	X
Drowsiness/somnolence (Days 1 to 7) †	X	X
Hives or welts/urticaria (Days 1 to 7) †	X	X
Appetite loss/decreased appetite (Days 1 to 7) †	X	X
Any AE ‡	X	X
Any Vaccine-related AE ‡	X	X
Any SAE ‡	X	X
Any Vaccine-related SAE ‡	X	X
Discontinuation due to AE ‡	X	X
Death ‡	X	X
Maximum temperature measurements meeting the Brighton Collaboration cut points (Days 1 to 7)	X	X

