Specific AEs by SOC and PT		X

AE = adverse event; CI = confidence interval; PT = preferred term; SAE = serious adverse event; SOC = system organ class; X = results will be provided.

† Includes solicited events only.

‡ These endpoints are broad adverse event categories. For example, descriptive statistics for the safety endpoint of “Any AE” will provide the number and percentage of participants with at least 1 AE.

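### Section 9.4.1 counts 'any AE' and 'vaccine-related AE' only on Days 1–7, although non-serious AEs are collected on Days 1–14; no Day 1–14 proportion is defined

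*Combined protocol and SAP*

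**What the plan says.** **Collection.** Three places set a 14-day period for non-serious AEs.
- Section 1.3 (Schedule of Activities, AE monitoring row): "Nonserious AEs are to be reported from Days 1 through 14 after each vaccination".
- Section 8.3.3, among the items parents enter on the report card: "Any other unsolicited injection-site or systemic AEs Day 1 through Day 14 postvaccination". Solicited AEs and temperature are entered for Days 1–7 only.
- Section 8.4.1 has the investigator report all AEs "from the day of each vaccination through 14 days postvaccination".

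**Analysis.** Section 9.4.1 lists proportions for the "broad AE categories consisting of any AE and a vaccine-related AE from Day 1 through Day 7 after any vaccination". The same list runs SAEs, vaccine-related SAEs, discontinuation due to an AE, and death through completion of participation.

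Section 9.6.2 says that "the broad AE categories consisting of the proportion of participants with any AE, a vaccine-related AE, an SAE, a vaccine-related SAE" and the remaining broad categories get exact (Clopper-Pearson) intervals, but it states no window for them. Table 4 writes Days 1 to 7 on each solicited row and on the temperature row, and nothing on the broad-category rows. Its last row, "Specific AEs by SOC and PT", has descriptive statistics only, with no interval and no window.

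**Elsewhere.** Section 4.1 describes follow-up for injection-site and systemic AEs through Day 7, without mentioning the 14-day collection. Section 4.2 says the endpoints and the length of safety follow-up agree with earlier pneumococcal conjugate vaccine studies. Section 4.2.1.2 says the safety endpoints rest on the product's safety profile, published data and regulatory guidance.

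**The concern.** The plan collects a second week of non-serious AEs after every dose, then defines its two overall AE proportions so that this week is left out. Section 9 has no separate endpoint for unsolicited AEs, which are the only non-serious AEs collected on Days 8–14. The general rationale in Sections 4.2 and 4.2.1.2 does not say why 7 of the 14 collected days are counted.

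At stake is how completely the overall AE summary describes the collected data. The first primary objective in Section 3 is framed as the proportion of participants with AEs, and a reader will take the 'any AE' row as the general answer. If that row stops at Day 7 while the SOC/PT table runs over all collected AEs, an infant can appear in the second table and be absent from the first, and the two displays will not reconcile. If the window is left open, it will be settled in programming, in an open-label study, possibly after the data have been seen.

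**Working it through.** **1. Windows side by side**

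| Item | Collected | Window in 9.4.1 | Window in Table 4 | 95% CI |
|---|---|---|---|---|
| Solicited AEs | Days 1–7 | Days 1–7 | Days 1–7 | yes |
| Temperature | Days 1–7 | Days 1–7 | Days 1–7 (maximum) | yes |
| Any AE; vaccine-related AE | non-serious: Days 1–14 | Days 1–7 | none stated | yes |
| SAE, vaccine-related SAE, death | through completion | through completion | none stated | yes |
| Discontinuation due to AE | AEs as above | through completion | none stated | yes |
| Specific AEs by SOC and PT | non-serious: Days 1–14 | not listed | none stated | no |

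Only the 'any AE; vaccine-related AE' line has an explicit analysis window shorter than its collection window. Take an infant whose only AE is non-serious and unsolicited, starts on Days 8–14, and does not lead to discontinuation. Under 9.4.1 that infant is counted in neither proportion. The event can appear only in the SOC/PT row, by term and without an interval.

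**2. The plan's own safety figures (Section 9.9.2, n = 45, all evaluable)**
- Chance of at least one SAE at 3.5%: 1 − 0.965^45 = 79.9% (stated 80%).
- Chance at 1.5%: 1 − 0.985^45 = 49.3% (stated 50%).
- Exact upper limit with no event: 1 − 0.025^(1/45) = 7.87% (stated below 7.9%).

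These reproduce to within a percentage point and confirm 45 as the safety denominator. The point does not depend on them.

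**3. What follows from the documents alone**
- One infant moves a proportion by 100/45 = 2.2 points.
- If all 45 infants receive all four doses, non-serious AEs are collected over 45 × 4 × 14 = 2,520 infant-days, of which 45 × 4 × 7 = 1,260 lie outside the Day 1–7 window. This counts calendar time, not events.

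**4. Illustration only**

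The documents give no AE rates. Let p7 be the Day 1–7 'any AE' proportion and q the chance per dose of a new AE on Days 8–14, taken as independent of the first week and between doses. Then

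rise = (1 − p7) × [1 − (1 − q)^4].

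| p7 | q | Rise | Infants of 45 |
|---|---|---|---|
| 95% | 2% | 0.05 × 0.0776 = 0.4 points | 0.2 |
| 95% | 10% | 0.05 × 0.3439 = 1.7 points | 0.8 |
| 80% | 5% | 0.20 × 0.1855 = 3.7 points | 1.7 |
| 60% | 2% | 0.40 × 0.0776 = 3.1 points | 1.4 |
| 60% | 10% | 0.40 × 0.3439 = 13.8 points | 6.2 |

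For scale, 36/45 = 80.0% (exact 95% CI 65.4 to 90.4) would become 38/45 = 84.4% (70.5 to 93.5). Every p7 and q here is assumed, and the top value pairs the lowest first-week proportion with the highest second-week chance.

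**The case against.** **Table 4 may already tabulate all collected AEs.** Section 9.1 sends the reader to 9.6.2 for the safety analysis strategy. Table 4 there puts Day 7 on the solicited and temperature rows and leaves it off the broad categories, and its footnote describes 'Any AE' simply as at least one AE. That is a fair reading, but it does not remove the problem: Table 4 would then contradict the explicit Day 7 limit in 9.4.1. Either way the text needs correcting.

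**The second week is largely covered.** A reader might infer that no overall proportion with an interval reaches Days 8–14, or that second-week events are lost. The documents do not support that. SAEs, vaccine-related SAEs, discontinuations due to AEs and deaths are also broad categories with exact intervals and run through completion, and SOC/PT summaries may still show the other events. What remains is non-serious, unsolicited AEs that do not lead to discontinuation. This limitation stands and sets the scope of the point.

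**A rationale exists.** It would be too strong to say that none is given, because Sections 4.2 and 4.2.1.2 offer a general one. It is not specific to Day 7 versus Day 14. The earlier studies are not available here, so a departure from their practice cannot be shown.

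**The primary endpoints are untouched.** This is correct. The endpoints listed against the first primary objective are solicited AEs on Days 1–7 and vaccine-related SAEs; neither of the two proportions at issue is among them. Nor is the Day 1–7 figure biased: it estimates a narrower quantity. No test, error rate or sample size is involved (Section 9.3).

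**Conclusion.** The mismatch holds on the text: 14 days collected, 7 counted, no Day 1–14 proportion defined, and no window in Section 9.6.2 or Table 4 to settle it. The consequence is modest, because only the remaining group of non-serious unsolicited events described above lacks an overall proportion with an interval.

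The size that the documents support is 2.2 points per affected infant, assuming the full safety denominator of 45. How many infants would be affected cannot be derived from them. The illustrated rises of 0.4 to 13.8 points rest wholly on assumed rates and on independence, and should not be read as expected effects. No estimate is possible for 'vaccine-related AE' without further assumptions. The correction is still worth making, since the data are already being collected and the window can be fixed before database lock.

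**What to change.** In Sections 9.4.1 and 9.6.2 and in Table 4, or in the sSAP that Section 9 provides for changes before database lock:

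1. Report 'any AE' and 'vaccine-related AE' for Day 1 through Day 14 after each vaccination, with exact 95% CIs. These may replace the Day 1–7 proportions or stand beside them; if both are kept, say what the Day 1–7 figure is for.
2. State the same Day 1–14 window for the SOC/PT table, so that it reconciles with the overall proportions.
3. Keep Days 1–7 for solicited AEs and temperature, which are collected only on those days.
4. Reconcile the Day 7 follow-up statement in Section 4.1 with the 14-day collection in Sections 1.3, 8.3.3 and 8.4.1.

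Section 9.6.2 allows safety to be summarised separately once the data at 30 days after the third dose are complete, so the window is best fixed before any such summary.

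The cost is wording. No visit, sample or test is added and the sample size does not change. The downside is slightly higher reported AE proportions or, if both windows are kept, two extra table rows.
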